8.3 Database management and quality control

Novartis staff (or CRO working on behalf of Novartis) review the data entered into the CRFs by investigational staff for completeness and accuracy and instruct the site personnel to make any required corrections or additions. Queries are sent to the investigational site using an electronic data query. Designated investigator site staff is required to respond to the query and confirm or correct the data.

Concomitant medications entered into the database will be coded using the WHO Drug Reference List, which employs the Anatomical Therapeutic Chemical (ATC) classification system. Concomitant procedures, non-drug therapies and adverse events will be coded using the Medical dictionary for regulatory activities (MedDRA) terminology.

For those laboratory samples that will be processed centrally the results will be sent electronically to Novartis (or a designated CRO). ECG readings will be processed centrally and the results will be sent electronically to Novartis (or a designated CRO).

Randomization codes and data about all study drug(s) dispensed to the patient will be tracked using an IRT. The system will be supplied by a vendor, who will also manage the database. The database will be sent electronically to Novartis (or a designated CRO).

The occurrence of relevant protocol deviations will be determined. After these actions have been completed and the database has been declared to be complete and accurate, it will be locked. Any changes to the database after that time can only be made after written agreement by Novartis Development management.

8.4 Safety review committee

A safety review committee will be established for this study to review patient safety at several time points. The safety review committee can recommend stopping the study or a specific treatment arm in case of serious safety observations especially related to hepatic safety profile. The safety review committee will include at least one external hepatologist. Regular interim review for patient safety will be performed during the study as specified in the safety review committee charter.

Additional ad-hoc safety review may be requested by the safety review committee or the Study Team if needed.

Details of safety analyses will be specified in the analysis plan for the safety review committee. The safety review committee will make recommendations to the Study Team on any safety issues that are deemed relevant and any changes in the conduct of the study.

Further details of the safety review committee's composition, organization and responsibilities will be described in the safety review committee charter.

8.5 Adjudication Committee

Not required.

9 Data analysis

At the end of trial, full statistical analyses will be performed by cohort and treatment group. Coartem data from all cohorts will also be pooled.

Any data analysis carried out independently by the investigator should be submitted to Novartis before publication or presentation.

9.1 Analysis sets

Randomized set

All patients who are randomized.

Full analysis set (FAS)

FAS will be comprised of all patients from Randomized set who take at least one dose of study treatment during the treatment period and whose baseline parasitaemia count is greater than 0. Following the intent-to-treat principle, patients will be analyzed according to the treatment group assigned to at randomization.

Safety set (SAF set)

Safety set includes all patients who take at least one dose of study drug during the treatment period. Patients will be analyzed according to treatment received. Full details will be described in the statistical analysis plan (SAP).

Per-protocol set (PPS)

PPS will be comprised of patients in FAS who

- did not have any important protocol deviations
- took at least 80% of assigned study medication(s). If a patient vomited the original dose but did not vomit the replacement dose, the patient is considered as taking the dose of study medication. Except for patients who are assigned to Coartem treatment, this requires that all patients take all KAE609 dosages as assigned

- did not take other antimalarial medications prior to Study Day 29 for reasons other than rescue medication given for *P. falciparum* related treatment failure, and
- met at least one of the following criteria: (a) classified as treatment failure before Study Day 8 (see [Section 6.5.8](#)), (b) absent from parasitaemia at Study Day 29, or (c) had valid PCR evaluations at baseline and at the time point with parasitaemia if parasitaemia is present at Study Day 8 or later.

Important protocol deviations for exclusion from PPS will be identified by the clinical team before the final database lock.

PK analysis set

All subjects in the safety analysis set who had evaluable PK parameter data and took at least 80% of assigned study medication.

9.2 Patient demographics and other baseline characteristics

Demographic data and baseline disease characteristics will be descriptively presented and tabulated (n, mean, standard deviation, median, minimum, and maximum for continuous variables; n and percent for categorical variables) per cohort and treatment arm, as well as overall, using the Randomized set.

9.3 Treatments

All analyses in this section will be performed using the safety set.

9.3.1 Study treatment

Number and percentage of doses taken will be presented by cohort and treatment arm. The percentage will be calculated based on the planned number of doses per treatment arm. Percentage of patients with study drug vomiting and dose replacement will be presented by treatment arm. Average daily dosage and total dosage (in mg or tablet) of each drug (KAE609, Coartem) will be summarized by cohort and treatment arm.

9.3.2 Prior and concomitant medication

Medications will be identified using the Novartis drug and therapy dictionary (NovDTD) including ATC code.

Prior and concomitant medications will be summarized by cohort and treatment group in separate tables. Concomitant rescue and other anti-malarial medications will also be summarized by cohort and treatment group. Medications will be presented by ATC class and preferred term. Tables will also show the overall number and percentage of subjects receiving at least one drug of a particular ATC class.

Prior medications are defined as drugs taken and stopped prior to first dose of study medication. Any medication given at least once between the day of first dose of randomized study medication and the last day of study visit will be a concomitant medication, including those which were started pre-baseline and continued into the treatment period.

9.4 Analysis of the primary variable(s)

The primary variable is a safety related endpoint. Therefore, it will be analyzed primarily using the SAF set. Efficacy variables are related to secondary [REDACTED] and the related analyses will be presented in [Section 9.5](#) and [Section 9.6](#).

9.4.1 Primary Variable(s)

The primary variable is the occurrence of at least 2 CTCAE grades increase from baseline in ALT or AST during the 4 weeks study period.

9.4.2 Statistical model, hypothesis, and method of analysis

The study is a Phase II safety study aiming to rule out high incidence of abnormal LFT reported in a couple of earlier studies. As the significance of safety related results is determined by both the frequency of the event and the severity of the event, there is no pre-defined hypothesis. The following analyses will be performed using the SAF set:

- Proportion of patients with occurrence of the primary variable by cohort and treatment group and the 95% confidence interval based on the exact CI (Pearson-Clopper method).
- 2-sided Fisher exact test for each KAE609 treatment group compared to the pooled Coartem.

These results along with patient narratives will be assessed to make decision about whether a KAE609 dosage regimen is safe for further development.

9.4.3 Handling of missing values/censoring/discontinuations

No missing value of the primary variable is expected since the analysis is based on the SAF set and all patients in the SAF set should provide safety observation as they are hospitalized for the first 3 days. No missing imputation will be done in this study.

9.4.4 Sensitivity analyses

In the past KAE609 studies, peak LFT occurred during the first 2 weeks. For patients who discontinued the study during the first 2 weeks, their peak LFT may not be observed. Analyses in [Section 9.4.2](#) will be performed by excluding those patient(s) who discontinued the study before Study Day 15 and did not experience at least 2 CTCAE grades increase from baseline in ALT or AST.

9.5 Analysis of secondary variables

Descriptive statistics for each secondary variable will be provided by cohort and treatment group. Statistical comparison with Coartem will not be performed due to small sample size for each treatment group.

9.5.1 Efficacy variables

Secondary efficacy variables include:

- PCR-corrected ACPR at Study Days 15 and 29;
- Uncorrected ACPR at Study Days 15 and 29;

- Proportion of patients with parasitaemia at 12, 24, and 48 hours after treatment;
- Parasite clearance time (PCT), defined as time from the first dose until the first total and continued disappearance of asexual parasite forms which remained at least a further 48 hours;
- Fever clearance time (FCT), defined as time from the first dose until the first time the axillary body temperature decreased below and remained below 37.5°C axillary or 38.0°C oral/tympanic/rectal for at least a further 24 hours;
- Proportion of patients with ETF;
- Proportion of patients with LCF;
- Proportion of patients with LPF;
- Incidence rate of recrudescence and reinfection at Study Day 29.

Analyses of ACPRs (PCR corrected or uncorrected) will be based on the FAS and PPS. Analyses of other secondary efficacy variables will be based on the FAS.

9.5.1.1 PCR-corrected ACPR and uncorrected ACPR

At each visit, the ACPR rate with 95% confidence intervals will be provided using the Pearson-Clopper method for each treatment group by cohort.

Data will be handled as follows:

- Treatment failures after 7 days (i.e., Study Day 8) due to reinfection based on PCR genotyping are not considered as failure for PCR-corrected analyses.
- For parasitological uncorrected ACPR, patients will be treated as failure on and after the visit when a new infection (i.e., reinfection) with *P. falciparum* or other species is detected.
- Patients who received rescue medication for the treatment of *P. falciparum* malaria (except for the treatment of a new infection) will be considered treatment failures. Patients who received other concomitant medication having an effect on malaria for reasons other than rescue therapy e.g., for the treatment of *P. vivax* (e.g., primaquine, certain antibiotics (sulfonamides, tetracycline, etc.)) will be considered in the analysis as if they had not taken the drug.
- Patients will be counted as failure at a visit (e.g., Study Day 15, etc.) if (a) they did not have a parasite count i.e., missing parasite count at that visit unless these patients could be classified as cured based on absence of parasitaemia (parasite count = 0) at a later time (e.g., Study Day 29), or (b) they did not have valid PCR evaluations at baseline and the visit if parasitaemia was present at that time (e.g., Study Day 15).

In addition, PCR-corrected ACPR rate will be calculated and plotted using the Kaplan-Meier method ([Stepniewska and White 2006](#); [WHO 2016](#)) for each treatment group by cohort in the FAS. Treatment failure is the event for analysis and patients without Study Day 29 data and treatment failure is considered as censored instead of treatment failure. The PCR-corrected ACPR rate at Study Day 29 is estimated by the survival function at Study Day 29. Patients who had a new infection (i.e., reinfection) with *P. falciparum* or other species without *P. falciparum* recrudescence on or after Study Day 8 will be censored at the time of the first PCR that indicate the infection; patients who took antimalarial medications for reinfection or reasons other than

rescue medication given for *P. falciparum* related treatment failure will be censored at the first time of such antimalarial medications; other patients without treatment failure will be censored at the time of last parasitaemia assessment.

9.5.1.2 Treatment failure related parameters

For the following parameters, 95% confidence intervals will be provided for each treatment group by cohort using the Pearson-Clopper method:

- proportion of patients with parasitaemia at 12, 24, and 48 hours after treatment
- proportion of patients with ETF
- proportion of patients with LCF
- proportion of patients with LPF

The above parameters will be determined using the uncorrected parasite counts.

In addition, patients whose outcome status cannot be determined due to incomplete/missing data will be excluded from analysis.

9.5.1.3 Parasite clearance time (PCT) and fever clearance time (FCT)

Descriptive statistics (mean, standard error, median, quartiles) will be presented for each treatment by cohort using the Kaplan-Meier method. Kaplan-Meier curves will be provided.

PCT will be calculated based on uncorrected parasite counts. Patients without parasite clearance for whatever reason will be censored at the time of last parasite assessment. Patients who were enrolled on the basis of history of fever and did not subsequently have a fever at pre-dose will not be included in the analysis of FCT. Patients without fever clearance for whatever reason will be censored at the time of last temperature assessment. In case that a patient receives rescue medication before (parasite or fever) clearance, the time to event will be censored at the first use of rescue medication.

9.5.1.4 Recrudescence

Reinfection is defined as appearance of asexual parasites after clearance of initial infection with a genotype different from those parasites present at baseline.

Recrudescence is defined as appearance of asexual parasites after clearance of initial infection with a genotype identical to that of parasites present at baseline. Recrudescence must be confirmed by PCR analysis.

Incidence rates of recrudescence at Study Day 29 will be estimated by Kaplan-Meier method based on the subset of FAS patients who have clearance of initial infection by Study Day 7. Time to recrudescence will be calculated from the time of first study medication to the date of first event if a patient experience the event and be censored at the time of last parasite assessment if a patient does not experience the event.

9.5.2 Safety variables

All safety parameters will be analyzed by cohort and treatment group based on the safety.

9.5.2.1 Adverse event

The number and percentage of patients who report adverse events will be provided according to primary system organ class (PSOC), preferred term, and severity. If a patient reports more than one adverse event with the same preferred term, the adverse event with the greatest severity will be presented. If a patient reports more than one adverse event within the same PSOC, the patient will be counted only once with the greatest severity.

Cause of death, SAEs, adverse event causing study drug discontinuation, adverse events by severity and causality will be presented. Listings of these events will be provided.

9.5.2.2 Laboratory evaluations

Summary of laboratory evaluations will be presented with respect to three groups of laboratory tests (hematology, blood chemistry, and urinalysis).

Descriptive summary statistics (mean, median, standard deviation, minimum and maximum) for the baseline, each study visit, and change from baseline to each study visit will be presented. These descriptive summaries will be presented by laboratory test group.

In addition, shift tables will be provided in order to compare a patient's baseline laboratory evaluation relative to each study visit and at the maximum value. For the shift tables, the normal laboratory values will be used to evaluate whether a particular laboratory test value is normal, low, or high for each visit value relative to whether or not the baseline value is normal, low, or high. For liver enzymes (ALT, AST, etc.), the shift table of CTCAE grades relative baseline and number and percent of patients with $\geq 2 \times$ ULN (if baseline is normal) or $2 \times$ baseline (if baseline is $>$ ULN) will be provided. These summaries will be presented by laboratory test group.

9.5.2.3 Vital signs

Descriptive summary statistics for the baseline, each study visit, and change from baseline to each study visit will be presented for each vital sign parameter (pulse rate, systolic/diastolic blood pressures).

Number and percentage of patients who have vital sign values that meet the criteria for being clinically notable after the first dose of study medication will be presented.

9.5.2.4 ECGs

[figure not shown]
[figure not shown]
Descriptive summary statistics for the baseline, each study visit, and change from baseline to each study visit will be presented for heart rate, PR interval, QRS interval, RR interval, QT interval and QTcF (QT interval corrected for heart rate according to Fridericia). Number and percentage of patients with abnormal values (such as QTc $>$ 480 ms and $>$ 500 ms or HR $<$ 50 /min) and changes from baseline (such as increases in QTc for ≥ 30 ms and ≥ 60 ms) will be tabulated at each time point and at the maximum value by treatment group in the form of a categorical analysis.

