5.6.2 Discontinuation of study treatment

Patients will be treated under hospital supervision during the treatment period. Discontinuation of study treatment for a patient occurs when study drug is stopped earlier than the protocol planned duration, and discontinuation can be initiated by either the patient or the investigator. For patients assigned to 1-day treatment arm, they will not be considered as treatment discontinuation if those discontinuation events occur after they have completed the treatment as assigned.

The investigator must discontinue study treatment for a given patient if, on balance, he/she believes that continuation would negatively impact the participation of the patient in the trial.

Study treatment must be discontinued under the following circumstances:

- Patient request
- Pregnancy (see [Section 6.5.6](#) and [Section 7.6](#))
- Use of prohibited treatment as per recommendations in [Section 5.5.8](#)
- Any situation in which study participation might result in a safety risk to the patient and/or any adverse events that in the judgment of the investigator, taking into account the patient's overall status, prevent the patient from continuing participation in the study
- Unsatisfactory therapeutic effect (see [Section 6.5.8](#))

- Emergence of the following adverse events: severe nausea/vomiting, severe pruritus, increases in QTcF to >500 ms (based on repeat Electrocardiograms (ECGs), development of ventricular arrhythmia or clinically significant (symptomatic) bradycardia (see [Appendix 3](#))
- Any laboratory abnormalities (e.g., LFT increase) that in the judgment of the investigator, taking into consideration the patient's overall status, prevent the patient from continuing taking the study medication (see [Appendix 2](#))
- Deviation from the planned dose regimen for the study drug

Patients who discontinue study drug for any of the above reasons may be given rescue medication at the discretion of the investigator and will be followed for the whole study duration until Study Day 29.

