### **2.8.1.1 Adverse events of special interest / grouping of AEs**

The adverse events of special interest are defined in the Case retrieval Sheet (CRS) which is updated for each MedDRA dictionary. The CRS data are stored in RDCRS SAS dataset corresponding to a subset of eCRS SAS view for which the following filtering criteria are applied

-Drug code = KAE609

-the latest version of MedDRA at the time of final database lock.

-End date is null (this means this is the latest CRS version)). Potential risks based on the current CRS are listed in [Table 2-1](#).

The number and percentage of patients with these special AEs will be summarized. In addition, listings of related adverse events will be provided.

Newly occurring liver enzyme abnormalities and QTcF (QT interval corrected for heart rate according to Fredericia) abnormalities will be summarized. Only QTcF and HR will be summarized for the intext table. QTcF will be summarized in post-text tables and will be presented in the listing. (see [Sections 2.8.2 and 2.8.3.1](#)).

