### 2.8.3 Other safety data

#### 2.8.3.1 ECG and cardiac imaging data

The following quantitative variables will be summarized for averaged triplicate ECG: heart rate, RR interval, PR interval, QRS interval, QT interval and QTcF. Summary statistics for change from baseline will be presented for ECG variables by timepoint and treatment group.

QT intervals will be summarized categorically by computing the number and percentage of patients at each time point and at the maximum post baseline value for the following categories:

- QT, QTcF
  - New  $> 450$  and  $\leq 480$  ms
  - New  $> 480$  and  $\leq 500$  ms
  - New  $> 500$  ms
  - Increase from baseline of  $> 30$  ms to  $\leq 60$ ms
  - Increase from baseline of  $> 60$  ms
- HR
  - Increase from baseline  $>25\%$  and to a value  $> 100$  bpm
  - Decrease from baseline  $>25\%$  and to a value  $< 50$  bpm
- PR
  - Increase from baseline  $>25\%$  and to a value  $> 200$  ms
  - New value of  $> 200$  ms

- QRS
  - Increase from baseline >25% and to a value > 120 ms
  - New > 120 ms

A line plot by patient (Spaghetti plot) will be provided by cohort, visit and treatment group.

In addition, shift tables comparing baseline ECG results (normal, abnormal, not available, total) with the post-baseline results will be provided by visit and at the worst post-baseline result (normal, abnormal, not available, total).

A listing of all newly occurring or worsening abnormalities will be provided, as well as a by-patient listing of all quantitative ECG parameters.

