**Table 5-7 Rules for flagging variables**

Timing of measurement	Type of data	Rule
Baseline	All data	The last measurement made prior to and including administration of the first dose of study treatment – note this may include measurements taken on the day of randomization. If a patient did not receive any dose of study treatment then the randomization date will be used.
Post-baseline efficacy	All data	The measurement closest to the target day/time will be used. In the event that two measurements are taken equally apart (e.g. 1 day before target date and 1 day after) the first one will be used.
Post-baseline safety	Summary visit information (e.g. lab, ECG, etc.)	The measurement closest to the target day/time will be used. In the event that two measurements are taken equally apart, the first one will be used.
Post-baseline safety	Notable abnormalities (e.g. lab, ECG, VS)	The most extreme measurement in the window will be used. Note this means a patient can have a notably high and notably low measurement within a window

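### The overall ECG row for low heart rate is taken at the maximum post-baseline value, the wrong extreme for a low-side criterion, so as written it would miss most patients with a low rate

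*Protocol*

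**What the plan says.** Protocol 9.5.2.4 gives examples of ECG abnormalities: QTc above 480 and 500 ms, heart rate below 50/min, and QTc increases of at least 30 and 60 ms. It says that all of them "will be tabulated at each time point and at the maximum value by treatment group in the form of a categorical analysis". No minimum is named for heart rate.

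SAP 2.8.3.1 says that QT intervals are to be summarised categorically "by computing the number and percentage of patients at each time point and at the maximum post baseline value for the following categories". The list that follows covers QT and QTcF and also heart rate, PR and QRS. One heart-rate category is a decrease of more than 25% from baseline to below 50 bpm.

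SAP Table 5-7 has a rule for notable abnormalities, naming ECG: "The most extreme measurement in the window will be used". It adds that a patient may be both notably high and notably low within one window.

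SAP Table 5-6 gives seven post-baseline ECG windows for KAE609 (4, 12, 24, 52, 60 and 72 h, and Day 29) and three for Coartem (6 h, 68 h and Day 29).

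**The concern.** A single summary rule covers criteria that point in opposite directions. For QT, QTcF, PR, QRS and heart-rate increases, the maximum asks whether the patient ever crossed the threshold. For low heart rate, it asks whether the patient stayed below the threshold at every post-baseline ECG, which is a different and much rarer event.

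The overall row matters because the ECG time-point rows do not line up between drugs: the end-of-study window is the only one that KAE609 and Coartem share in Table 5-6. Comparing ECG bradycardia between KAE609 and Coartem therefore depends largely on the overall row. A row near zero in every arm could be taken as evidence that low rates did not occur.

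**Working it through.** The plan gives no expected bradycardia rate and no heart-rate distribution, so it has no figure to reproduce. The check has a logical part, which needs no assumptions, and an illustration, which does.

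**1. What the row counts.** Let H1,…,Hk be a patient's post-baseline ECG heart rates.
- Protocol criterion at the maximum: max(H) < 50, so every rate must be below 50.
- Protocol criterion at the minimum: min(H) < 50, so at least one rate must be below 50.
- SAP criterion with baseline b: H < 50 and H < 0.75b, which is H < c with c = min(50, 0.75b). Since 50/0.75 = 66.7, c is 50 for baselines of about 67 bpm or more and lower otherwise (b = 60 gives c = 45). For each patient this is still one low-side cut-off, so the same maximum/minimum argument applies.

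Example: baseline 78, a rate of 44 at 12 h, and 78 at every other ECG. The fall is (78 − 44)/78 = 43.6%, to below 50, so both criteria are met at 12 h. The maximum is 78, so the overall row does not count this patient.

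**2. Effect of the number of ECGs.** One more ECG can only raise the maximum or leave it unchanged. For the same underlying heart rates, an arm with more ECGs therefore shows an equal or smaller count in the overall row.

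**3. Whether Table 5-7 repairs it.** That rule chooses a value inside one analysis window. The overall row is formed across windows, and SAP 2.8.3.1 calls that value the maximum. Table 5-7 does not define it.

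**4. Illustration of size (assumptions not in the documents).** Heart rate is normal with SD 10 bpm, mean μ of 62, 68 or 75, and within-patient correlation ρ of 0.3, 0.5 or 0.8. Model: H = μ + 10(√ρ·b + √(1−ρ)·e), where b here is a standard normal patient effect and e standard normal error. There are 500,000 simulated patients per setting, with k = 7 or 3 windows. Only the protocol's below-50 criterion is used. Share missed = 1 − P(max < 50)/P(min < 50).

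| μ | ρ | k=7: min<50 | k=7: max<50 | k=7: missed | k=3: min<50 | k=3: max<50 | k=3: missed |
|---|---|---|---|---|---|---|---|
| 62 | 0.3 | 45.6% | 0.07% | 99.9% | 27.3% | 0.92% | 96.6% |
| 62 | 0.5 | 38.1% | 0.42% | 98.9% | 24.6% | 2.01% | 91.8% |
| 62 | 0.8 | 26.2% | 2.66% | 89.8% | 19.4% | 4.86% | 75.0% |
| 68 | 0.3 | 18.8% | 0.00% | 100% | 9.6% | 0.10% | 99.0% |
| 68 | 0.5 | 15.6% | 0.04% | 99.8% | 8.7% | 0.28% | 96.8% |
| 68 | 0.8 | 10.1% | 0.50% | 95.1% | 6.9% | 1.12% | 83.7% |
| 75 | 0.3 | 3.9% | 0.00% | 100% | 1.8% | 0.00% | 99.9% |
| 75 | 0.5 | 3.4% | 0.00% | 100% | 1.7% | 0.02% | 98.8% |
| 75 | 0.8 | 2.2% | 0.05% | 97.7% | 1.4% | 0.12% | 91.0% |

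The literal row misses about 90% or more with seven windows and about 75% or more with three. In absolute terms, for an arm of 20 with seven windows, the patients with any rate below 50 number about 2.0 to 3.8 at mean 68 (20 × 10.1% to 20 × 18.8%), but only 0.4 to 0.8 at mean 75 (20 × 2.2% to 20 × 3.9%).

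**The case against.** The strongest reply is that the wording was meant for QT and that no competent programmer would take the highest rate to flag bradycardia. The SAP sentence does open with QT intervals, and Table 5-7 shows an intention to capture extremes in both directions. The same SAP section also uses the direction-neutral idea of a worst post-baseline result for its normal/abnormal shift table. This is fair evidence of intent, and it means the undercount follows from the literal reading and is not certain to occur. It does not settle the specification, because the low-rate category sits under that sentence and nothing else defines the across-visit row.

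The reply is also right about consequences. A reader might infer that bradycardia would vanish from the report, or that this row is the only per-patient count. The documents do not support either.
- Time-point rows and the listings of new or worsening ECG abnormalities are unaffected. So is the worst-result shift table, although it shows only normal or abnormal.
- Protocol 9.5.2.3 and SAP 2.8.3.2 with Table 2-3 plan a separate per-patient count of pulse at or below 50 bpm with a fall of at least 15 bpm. Table 5-5 gives it the same visit windows in all arms. It is a different measurement and criterion, but it is a per-patient low-rate count.
- Adverse events, including those leading to discontinuation, are summarised per patient regardless of this row.

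Two further inferences go too far. SAP 2.8.1.1 says "Only QTcF and HR will be summarized for the intext table", but not that the in-text table uses the maximum row or a low-rate category. Protocol 5.6.2 lists "development of ventricular arrhythmia or clinically significant (symptomatic) bradycardia" as grounds for stopping treatment; that concerns symptomatic bradycardia and does not depend on a tabulated rate below 50.

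Finally, the illustration rests on assumed distributions and omits the SAP's condition of a fall of more than 25%. The seven-window case may not apply in full to one-day regimens.

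**Conclusion.** The point holds as a specification error of limited reach. Both documents evaluate a low-side heart-rate criterion at the maximum, and no other text corrects the overall row. Read as written, the row counts only patients whose every post-baseline rate meets the low criterion, so it would miss most patients with a low ECG rate and would tend to count fewer in the more often monitored KAE609 arms. That direction follows from the wording alone.

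The size does not. About three quarters or more missed is the range under the assumed distributions and the below-50 criterion only, and the absolute number of patients affected could be below one per arm. A statement that the study will report almost no bradycardia would go beyond the documents. The table is secondary and descriptive, with no hypothesis test. The primary hepatic endpoint and the liver-based escalation rules are untouched.

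**What to change.** In Protocol 9.5.2.4 and SAP 2.8.3.1, replace the reference to the maximum with the most extreme post-baseline value in the direction of the criterion: the minimum for low heart rate, and the maximum for QT, QTcF, PR, QRS and heart-rate increases. State that the direction-specific rule of SAP Table 5-7 also applies to the overall post-baseline row. For the SAP category, evaluating the minimum is enough, because the fall of more than 25% and the value below 50 bpm are both met at the minimum whenever they are met together at any ECG.

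If the protocol is not amended, record the change in SAP section 4, which currently lists none. The cost is one phrase in each document and one line of programming, with no new data.
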